# 10. DEMOGRAPHICS AND OTHER BASELINE CHARACTERISTICS

In general, all tables presented in CSR section 14.1 should show a Total column across vaccine groups.

# 10.1 Demographics

Age, height, weight, body mass index at enrolment in this extension study will be summarized by reporting the mean, standard deviation, median and range, and will be calculated by vaccine group and overall.

The frequencies and percentages of subjects by sex, country, age categories (for posting), ethnic origin, entry criteria fulfilled will be presented by vaccine group and overall. Demographic data will be tabulated for the All Enrolled, FAS persistence, PPS persistence, and Safety sets.

Demography and baseline characteristics at time of enrolment in parent study (V102\_15) will also be reported (by vaccine group), in the subset of subjects from Poland and Finland, in the 4 vaccine groups of interest (ABCWY\_0\_2, ABCWY\_0\_6, ABCWY\_0\_2\_6, B\_0\_2), separately for subjects subsequently enrolled and not enrolled in this current extension study (V102\_15E1).

# 10.2 Medical History

The frequencies and percentages of subjects with medical history will be presented by MedDRA system organ class and preferred term, by vaccine group and overall. Medical history data will be tabulated for the All Enrolled.

## 11. IMMUNOGENICITY ANALYSIS

# 11.1 Blood Samples

The frequencies and percentages of subjects with blood draws will be summarized overall and by vaccine group. Data will be tabulated for the enrolled set.

# 11.2 Primary Objectives Analysis

1. To assess the persistence of bactericidal antibodies in subjects who previously received 2 or 3 doses of MenABCWY (administered according to 0, 2-, 0, 6- and 0, 2, 6-month schedules) or 2 doses of rMenB+OMV (given at a 0, 2-month schedule), at 24 months after the last meningococcal vaccination in study V102\_15 compared with baseline antibody levels in meningococcal naive subjects at enrolment, as measured by percentages of subjects with HT-hSBA titers ≥ LLOQ and HT-hSBA GMTs against N. meningitidis test strains for serogroup B and serogroups A, C, W, and Y.

# 11.3 Secondary Objectives Analysis

- 1. To assess the immune response at Day 31 after a booster dose of the MenABCWY vaccine given 24 months after last meningococcal vaccination in subjects who previously received 2 or 3 doses of MenABCWY at different schedules (administered according to 0, 2-, 0, 6- and 0, 2, 6-month schedules) in study V102\_15 compared with the immune response at Day 31 after a single dose of MenABCWY in naive subjects, as measured by percentages of subjects with HT-hSBA titers ≥ LLOQ, percentages of subjects with four-fold rise in titers and HT-hSBA GMTs against *N. meningitidis* serogroups A, C, W, Y and serogroup B test strains;
- 2. To assess the immune response at Day 1 (prevaccination), and at Day 6 and Day 31 after a booster dose of MenABCWY given at 24 months after last meningococcal vaccination in subjects who previously received 2 or 3 doses of MenABCWY at different schedules (administered according to 0, 2-, 0, 6- and 0, 2, 6-month schedules) in study V102 15, and at Day 1 (prevaccination) and after

 Serogroup B test strains to be used in the study: NZ98/254 (PorA), M14459 (fHbp), M07-0241084 (NHBA) and 96217 (NadA).

<sup>7 For subjects with prevaccination hSBA titers < LLOQ, a post-vaccination hSBA  $\geq$  4 times the LLOQ; for subjects with prevaccination hSBA titers  $\geq$  LLOQ, an increase of at least 4 times the prevaccination hSBA.

2 doses of MenABCWY (at Day 66 and Day 91) in naive subjects, as measured by percentages of subjects with HT-hSBA titers ≥ LLOQ, percentages of subjects with four-fold rise in titers and HT-hSBA GMTs against *N meningitidis* serogroups A, C, W, Y and serogroup B test strains;

- 3. To assess the immune response at Day 31 after a booster dose of the rMenB+OMV vaccine given 24 months after last meningococcal vaccination in subjects who previously received 2 doses of rMenB+OMV administered according to 0, 2-month schedule in study V102\_15 compared with the immune response at Day 31 after a single dose of rMenB+OMV in naive subjects, as measured by percentages of subjects with HT-hSBA titers ≥ LLOQ, percentages of subjects with four-fold rise in titers and HT-hSBA GMTs against *N. meningitidis* serogroup B test strains;
- 4. To assess the immune response at Day 1 (prevaccination), and at Day 6 and Day 31 after a booster dose of the rMenB+OMV vaccine given 24 months after last meningococcal vaccination in subjects who previously received 2 doses of rMenB+OMV at 0, 2-month schedule in study V102\_15, and at Day 1 (prevaccination) and after 2 doses of rMenB+OMV (at Day 66 and Day 91) in naive subjects, as measured by percentages of subjects with HT-hSBA titers ≥ LLOQ, percentages of subjects with four-fold rise in titers and HT-hSBA GMTs against *N. meningitidis* serogroup B test strains.

## Analysis Sets

The analysis set to be used for all secondary immunogenicity objectives is the Full Analysis Set. Analysis of the objectives will, in any case, be based on both the Full Analysis Set and the Per Protocol Set.

#### Statistical Methods

For each *N. meningitidis* serogroup B test strain (NZ98/254, M14459, M07-0241084 and 96217) the percentages of subjects with HT-hSBA titers ≥ LLOQ and the corresponding exact two-sided 95% CIs based on Clopper-Pearson method will be calculated at Day 1, Day 6 and Day 31 (follow-on) / Day 1, Day 66 and Day 91 (naive). Percentages and the

<sup>8 For subjects with prevaccination hSBA titers < LLOQ, a post-vaccination hSBA  $\geq$  4 times the LLOQ; for subjects with prevaccination hSBA titers  $\geq$  LLOQ, an increase of at least 4 times the prevaccination hSBA.  Serogroup B test strains to be used in the study: NZ98/254 (PorA), M14459 (fHbp), M07-0241084 (NHBA) and 96217 (NadA).

corresponding CIs will also be computed for subjects who are positive for at least one test strain, at least two test strains, at least three test strains, and all four test strains. The CIs for the rate difference will be constructed using the method of Miettinen and Nurminen (Miettinen and Nurminen, 1985).

The hSBA titers at each visit for each study group will be logarithmically transformed (base10) to fulfill the normal distribution assumption. For each *N. meningitidis* serogroup B test strain (NZ98/254, M14459, M07-0241084 and 96217), the GMTs and GMRs (post vaccination / pre-vaccination) will be calculated with their associated two-sided 95% CIs, by exponentiating the corresponding log-transformed means and their 95% CIs. Percentages of subjects with four-fold titer rise, the percentages of subjects with hSBA titers ≥ LLOQ and the corresponding exact two-sided 95% CIs based on the Clopper-Pearson method against these strains will be calculated for each study group at Day 1, Day 6 and Day 31 (follow-on) / Day 1, Day 66 and Day 91 (naive). The ratio of GMTs and GMRs between the two study groups and the corresponding CI will be constructed by exponentiating the mean difference and the confidence limits in log10 (titer), using ANOVA with study center included as an independent variable. The CIs for the rate difference will be constructed using the method of Miettinen and Nurminen. In addition, a reverse cumulative distribution plot of each measure will be created.

For each *N. meningitidis* serogroup A, C, W and Y, the GMTs and GMRs (post vaccination / pre-vaccination) will be calculated, with their associated two-sided 95% CIs, by exponentiating the corresponding log-transformed means and their 95% CIs. The percentages of subjects with hSBA titers against *N. meningitidis* serogroups A, C, W and Y and the corresponding exact two-sided 95% CIs based on Clopper-Pearson method for each treatment group will be summarized. Two-sided 95% Clopper-Pearson CIs for the percentages will be computed at Day 1, Day 6 and Day 31 (follow-on) / Day 1, Day 66 and Day 91 (naive). The ratio of GMTs and GMRs between the two study groups and the corresponding CI will be constructed by exponentiating the mean difference and the confidence limits in log10 (titer), using ANOVA with study center included as an independent variable. The CIs for the rate difference will be constructed using the method of Miettinen and Nurminen. In addition, a reverse cumulative distribution plot of each measure will be created.

#### 12. EFFECTIVENESS ANALYSIS

# 12.1 Primary Objectives Analysis

NA

12.2 Secondary Objectives Analysis

NA

### 12.3 Exploratory Objectives Analysis

NA

#### 13. SAFETY ANALYSIS

The analysis of safety assessments in this study will include summaries of the following categories of safety data collected for each subject:

- Vaccine exposure.
- Solicited local and systemic adverse events and indicators of solicited adverse events.
- Unsolicited adverse events.

#### 13.1 Analysis of Extent of Exposure

The frequencies and percentages of subjects with vaccinations will be summarized overall and by vaccine group. Data will be tabulated for the All Enrolled Set.

#### 13.1.1 Safety Completeness Analysis

#### Solicited adverse events

The safety completeness analysis on solicited adverse events aims to identify subjects who completed diary cards, irrespective of severity. The analysis will show the number of subjects with *valid data* by solicited adverse event and time point. *Valid data* in the context of the safety completeness analysis are all data entered in the diary card (including implausible values) except "Not done/unknown".

Four summaries will be produced:

- 1. The frequencies of subjects who provide diary cards by vaccine group.
- 2. For each solicited adverse event, the frequencies of subjects with *valid data* will be presented by vaccine group and timepoint: 30 min, 6h, days 2, 3, 4, 5, 6 and 7.
- 3. For each type of solicited adverse event (local, systemic) and indicators of solicited adverse events, such as analgesic use the frequencies of subjects *with valid data* by vaccine group, aggregated over time points: 6h day 7.

4. For each solicited adverse event, the frequencies of subjects *with valid data* by vaccine group, aggregated over time points: 6h - day 7.

For the corresponding percentages, the denominator will be the respective numbers of exposed subjects, i.e., subjects who received a vaccination and were still in-study for that time point or time interval, irrespective of whether a ediary card was present or not.

All analyses will be based on the 'as treated' analysis set.

# 13.2 Solicited Local and Systemic Adverse Events

For details please refer to section 7.1.1 of the protocol.

Only solicited local and systemic adverse events reported in the diary card will be analyzed. Implausible measurements will not be taken into consideration in the analysis but listed in the Appendix (see section 6.3).

Solicited adverse events will be reported at 30 minutes, at 6 hours on day 1 and then daily until day 7 using structured diaries. The analyses of solicited adverse events will be done separately for 30 minutes and based on three intervals: 6h - day 3, day 4 - 7 and 6h - day 7, each without 30 minutes data. In addition solicited adverse events ongoing after day 7 will be presented as unsolicited AE.

For erythema and induration, recorded originally as diameters (mm), the following categorization will be used to summarize the data:

Body temperature will be broken down by route of measurement according to the recommendations of the Brighton collaboration and will be summarized according to the 3 schemes described below:

- by 0.5 °C increments:
- <36.0.
- 36.0 36.4
- 36.5 36.9
- 37.0 37.4
- 37.5 37.9
- 38.0 38.4
- 38.5 38.9
- 39.0 39.4
- 39.5 39.9
- ≥40.0°C

- by 1.0 °C increments:
  - o <36.0**.**
  - 0 36.0 36.9
  - 0 37.0 37.9
  - 0 38.0 38.9
  - 0 39.0 39.9
  - o ≥40.0°
  - $<38.0, \ge38.0$  °C

Fever, defined as a body temperature of ≥38°C irrespective of route of measurement, will be integrated to the summaries as a systemic adverse event.

The analyses will encompass summaries of the data on five levels:

- 1. Daily reports of subjects with solicited adverse events (excluding 30 minutes on day 1).
- 2. Time of first onset of solicited adverse events (excluding 30 min measurement).
- 3. Solicited adverse events, maximum event severity by event and interval 6h day 3, day 4 -7, and 6h day 7, each without 30 min.
- 4. Duration of solicited adverse events, excluding ongoing AE after Day 7.
- 5. Solicited adverse events and indicators of solicited adverse events, occurrence of at least one event by category (local, systemic) and interval 6h-Day 3, Day 4-7 and 6h-Day 7, each without 30 min.

For each of the time points or time intervals presented in the summaries, only subjects with at least one plausible observation (i.e., any non-missing values but excluding "Not done/unknown" and implausible values) for the solicited adverse events in the interval of interest will be considered. Subjects without plausible data (i.e. missing values or reported as "Not done/unknown" and implausible values) will be removed from the denominator to prevent a downward bias (towards zero).

The analysis of solicited AE after first vaccination (applicable to all vaccine groups) will be reported separated from the analyses of solicited AE after second vaccination and after any vaccination (applicable only to naive subjects).

# Level 1: Daily reports of solicited adverse event

For each of the time points only subjects with at least one plausible observation (i.e., any non-missing values but excluding "Not done/unknown" and implausible values) for the solicited adverse event in the interval of interest will be considered. Subjects without plausible data (i.e. missing values or reported as "Not done/unknown" and implausible values) will be removed from the denominator in order to prevent a downward bias (towards zero). Data collected will be summarized (frequencies and percentages of subjects) by vaccine group, solicited adverse event, vaccination number and time point.

# Level 2: Time of first onset of solicited adverse events

The **time of first onset** is defined, for each subject, for each solicited adverse event, as the time point at which the respective solicited adverse event first occurred. For erythema, and induration the following threshold will be used  $\geq 25$  mm. The summary will provide the frequencies and percentages of subjects with first onset of each solicited adverse events by vaccine group and by each time point.

For each vaccination the first onset of the adverse event will be used for each subject. For any vaccination the worst adverse event across all vaccinations per time point will be used. Note, 'not done' is treated identical to 'missing'.

# Level 3: Solicited adverse events, maximum event severity by event and interval

The **maximum event severity** will be defined if there is at least one plausible non-missing observation (excluding "Not done/unknown" and implausible values) within this time interval, Each subject's data will be aggregated across the time points of the interval and summarized according to the maximal severity observed for each adverse event, followed by a summary across subjects for each vaccine. Subjects without any solicited adverse events in the interval, i.e., missing values at each of the requested time points, will be removed from the denominator.

### Level 4: Number of days with solicited adverse events

The number of days with the adverse event is defined irrespective of severity. This means at least 'mild' solicited adverse event that are assessed qualitatively  $\geq 25$ , mm for erythema and induration. If a solicited adverse event continues beyond day 7 the period after day 7 is not added.

The frequency distribution of the number of days will be provided in a summary table by vaccine and by adverse event.

Level 5: Solicited adverse events, occurrence of at least one event by category (local, systemic) and interval.

The **occurrence of at least one solicited adverse event** is defined as "any" for a subject if he/she reports greater than "none" ≥ 25 mm, for erythema, and induration) for the respective event and "none" otherwise. The occurrence of at least one solicited adverse event (i.e., none versus any) will be summarized by category (i.e., local, systemic, any), by vaccine group, by vaccination (after each vaccination and after any vaccination) and by time interval.

Medications to treat or prevent pain or fever will be summarized by frequencies and percentages of subjects reporting use of the medications by interval 30 min, 6h - day 3, day 4 - 7, 6h - day 7.

#### 13.3 Unsolicited Adverse Events

All the unsolicited adverse events occurring during the study, judged either as probably related, possibly related, or not related to vaccination by the investigator, will be recorded. The original verbatim terms used by investigators to identify adverse events in the CRFs will be mapped to preferred terms using the MedDRA dictionary. The unsolicited adverse events will then be grouped by MedDRA preferred terms into frequency tables according to system organ class. Adverse events judged by the investigator as at least possibly related to study vaccine will be summarized by vaccine group, according to system organ class and preferred term within system organ class. When an unsolicited adverse event occurs more than once for a subject, the maximal severity and strongest relationship to the vaccine group will be counted.

Only vaccine-emergent adverse events (see section 8.7 for definition) will be analyzed, i.e., excluding those after a subject has given informed consent but before vaccination. The selection of unsolicited adverse events and the assignment to time intervals will be done by day of onset and not by days ongoing/persisting.

The analysis of unsolicited adverse events comprises the following categories:

- Any unsolicited adverse event (from day 1 to day 31 all vaccine groups, from day 61 to day 91 and after any vaccination (day 1-31 and day 61-91) for naive groups only)
- Possibly or probably related unsolicited adverse events (from day 1 to day 31 all vaccine groups, from day 61 to day 91 and after any vaccination (day 1-31 and day 61-91) for naive groups only)
- Unsolicited adverse events leading to death (from day 1 to end of study for all vaccine groups).

- Serious adverse events (from day 1 to end of study for all vaccine groups).
- Possibly or probably related serious adverse event (from day 1 to end of study for all vaccine groups).
- Unsolicited adverse events leading to premature withdrawal from study (from day 1 to end of study for all vaccine groups).
- Unsolicited adverse events leading to dose reduction, interruption or delay in study vaccination (from day 1 to end of study for all vaccine groups).
- Medically attended adverse events (from day 1 to end of study for all vaccine groups).

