- Naïve controls: approximately 200 subjects who are meningococcal vaccinenaive and of similar age to subjects enrolled from the parent study,

approximately 12 to 20 years old, and will receive either 2 doses of MenABCWY or rMenB+OMV in the extension study.

Table 1: Study Groups in V102 15E1

	02_15 ry Study)	V102_15E1 ~24 months after last meningococcal vaccination in parent study				
Group	Group Vaccine (schedule)		Number of Subjects*			
ABCWY_0_2	ABCWY_0_2 MenABCWY (0, 2 months)		up to 196			
ABCWY_0_2_6	MenABCWY (0, 2, 6 months)	ABCWY_0_2_6	up to 130			
B_0_2	rMenB+OMV (0, 2 months)	B_0_2	up to 196			
ABCWY_0_6	MenABCWY (0, 6 months)	ABCWY_0_6	up to 130			
		Naive (freshly enrolled)	200			

^{*}Maximum enrolment derived from planned enrolment per group in parent trial

Duration of the study: The study duration is 180 days for all follow-on subjects, and 240 days for naive subjects.

Data collection: eDiary; electronic Case Reporting Form (eCRF).

The study comprises 3 clinic visits (at **D**ays 1, 6 and 31) and 3 safety phone calls (at **D**ays 16, 91 and 181) for follow-on subjects, as detailed in Table 2.

Table 2: V102_15E1 Blood Draw and Vaccination Schedule for follow-on subjects

		Target		Day 1	Day 6	Day 16		Day 31	Day 91	Day 181
Group	enrolment	Blood Draw	Vaccination	Blood Draw		Blood Draw		Phone Call for Safety Assessment		
	ABCWY_0_2	100	20 mL	MenABCWY	20 mL	Safety	20 mL			Phone Call for Safety
	B_0_2	100	20 mL	rMenB+OMV	20 mL	Phone call	20 mL	Safety Evaluation		Assessment and Study
	ABCWY_0_2_6	100	20 mL	MenABCWY	20 mL		20 mL			Termination
	ABCWY_0_6	100	20 mL	MenABCWY	Z 20 mL		20 mL			

Naive subjects will have 5 clinic visits (at **D**ays 1, 31, 61, 66 and 91) and 4 safety phone calls (at **D**ays 16, 76, 151 and 241), as detailed in Table 3.

Table 3: V102 15E1 Blood Draw and Vaccination Schedule for Naive subjects

			Day 1	Day 16	Day 31	Day 61	Day 66	Day 76	D	ay 91	Day 151	Day 241	
	N	Bloo d Dra w	Vaccinatio n	Safet	Bloo d Dra w	Vaccinatio n	Bloo d Dra w	Safet	Bloo d Dra w	Safety	Phone Call for Safety Assessme	Phone Call for Safety Assessme	
Naive_ABC WY	10 0	20 mL	MenABC WY	Phon e call	Phon	20 mL	MenABC WY	20 mL	Phon e call	20 mL	Evaluati on	nt	nt and Study
Naive_B	10 0	20 mL	rMenB+O MV		20 mL	rMenB+O MV	20 mL		20 mL			Terminati on	

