Safety Assessment: After vaccination at **D**ay 1 (and **D**ay 61 for naive subjects), subjects or their parents/legal guardians will be observed for at least 30 minutes at the clinic, and instructed to record any local and systemic AEs for 7 days after vaccination using eDiary. Unsolicited AEs will be collected for 1 month after each vaccination. SAEs, medically attended AEs and AEs leading to withdrawal will be collected for the duration of the study (180 days for follow-on subjects and 240 days for naive). Final safety assessment will be performed at Day 181 for follow-on subjects and Day 241 for naive subjects via a phone call.

Study termination: Subjects in the follow-on groups will be terminated after final safety assessment at **D**ay 181, while subjects in the Naive group will be terminated after final safety assessment at Day 241.

Randomization: an Interactive Response Technology (IRT) will be used in the study. The following randomization process will be used in this study.

1. Randomization into the treatment group only for the Naive group subjects

At Visit Day 1, prior to the study vaccination, naive subjects will be randomized into the 2 study groups according to a 1:1 ratio, MenABCWY: rMenB+OMV.

(Amended 4 April 2018)

Study Vaccines:

GSK Meningococcal ABCWY Vaccine (MenABCWY): Fixed-combination vaccine obtained by reconstitution and extemporaneous mixing of lyophilized MenACWY powder with liquid rMenB + OMV suspension for injection in deltoid muscle. The total volume for injection is ≥ 0.5 mL of solution.

GSK Meningococcal B Recombinant vaccine (rMenB+OMV): Each dose contains recombinant Neisseria meningitidis group B NHBA fusion protein (50μg), Recombinant Neisseria meningitidis group B NadA protein (50μg), Recombinant Neisseria meningitidis group B fHbp fusion protein (50μg), Outer membrane vesicles (OMV) from Neisseria meningitidis group B strain NZ98/254 (25μg) and Aluminum hydroxide (1.5 mg). Vaccine supplied as a single 0.5 mL dose administered IM into the deltoid area according to the relevant EU and US Summary of Product Characteristics.

Endpoint(s):

Primary Immunogenicity Endpoints

The following will be summarized at 24 months after last meningococcal vaccination for all follow-on subjects and at Day 1 in extension study for naive subjects

- Percentages of subjects with HT-hSBA titers ≥ LLOQ against each of four serogroup B test strains, and serogroups A, C, W and Y (only for MenABCWY groups).

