2.2.2 Secondary Safety Objectives

- 1. To evaluate safety and reactogenicity of a booster dose of MenABCWY given 24 months after last meningococcal vaccination in subjects who previously received 2 or 3 doses of MenABCWY at different schedules (administered according to 0, 2-, 0, 6- and 0, 2, 6-month schedules) in study V102_15, and after a first dose of MenABCWY in naive subjects;
- 2. To evaluate safety and reactogenicity of a booster dose of rMenB+OMV given 24 months after last meningococcal vaccination in subjects who previously received 2 doses of rMenB (administered according to 0, 2-month schedule) in study V102_15 and after a first dose of rMenB+OMV in naive subjects;

¹ For subjects with prevaccination hSBA titers < LLOQ, a post-vaccination hSBA \geq 4 times the LLOQ; for subjects with prevaccination hSBA titers \geq LLOQ, an increase of at least 4 times the prevaccination hSBA ² Serogroup B test strains to be used in the study: M14459 (fHbp), 96217 (NadA), NZ98/254 (PorA), and M07-0241084 (NHBA)

3. To evaluate safety and reactogenicity of 2 doses of MenABCWY or rMenB+OMV in naive subjects.

(Amended 4 April 2018)

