Vaccination allocation: For naive subjects, interactive response technology (IRT) will randomly assign 1 dose of MenABCWY or rMenB+OMV, based on a 1:1 ratio. IRT will automatically schedule a second visit on Day 61 for naive subjects to receive a second dose of the same vaccine received on Day 1.

No randomization to treatment arm for follow-on subjects is required as vaccine groups remain the same as in the parent study V102_15; however, vaccine allocation for follow-on groups will also be managed using IRT.

Block randomization will be used and within each block the treatments will be balanced.

Blinding: This is an open-label study.

Data collection: electronic Case Reporting Form (eCRF).

Study visits:

Follow on subjects: total of 3 clinic visits at Day 1, Day 6 and Day 31.

PRO-01 TEMP 06 / Atlas No. 293620 Version No.4 / Version Date: January 29, 2015 Naive subjects: total of 5 clinic visits at Day 1, Day 31, Day 61, Day 66 and Day 91.

Safety phone calls: Three safety phone calls (at Day 16, 91 and 181 for the follow on subjects and at Day 16, 76, 151 and 241 for the naive subjects) to collect medically-attended AEs, AEs leading to study withdrawal, SAEs and related medications and vaccinations.

(Amended 4 April 2018)

Written informed consent will be obtained from the subjects or from the parent or guardian according to the local regulations and GCP of the subject before conducting any study-specific procedures.

After signing informed consent, undergoing review of medical history, physical examination, prior medications/vaccination review, and confirmation of subject eligibility, subjects will be enrolled into the study.

Vaccination procedures: for the follow on subjects one IM injection on Visit Day 1 for the naive subjects two IM injections on Visits Day 1 and Day 61; one dose of the study vaccine will be administered each visit in the deltoid area of non-dominant arm for the naive subjects.

Post-vaccination evaluation:

Safety assessments of the subjects after vaccination will include:

- An observation period at the clinic for at least 30 minutes after each study vaccination. At 30 minutes post-vaccination, solicited local and systemic AEs, any unsolicited AE and body temperature will be recorded in source documents and eCRF.

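### For SAEs, medically attended AEs and AEs leading to withdrawal, the SAP's single Day 1 to end-of-study window does not isolate the naive first dose named in safety objectives 1 and 2

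*SAP*

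**What the plan says.** SAP 13.3 lists the unsolicited-AE categories and the period for each. Three of them have one long window. The SAE entry reads "Serious adverse events (from day 1 to end of study for all vaccine groups". The entry on withdrawals has the same period: "Unsolicited adverse events leading to premature withdrawal from study (from day 1 to end of study for all vaccine groups". So does a third, which reads "Medically attended adverse events (from day 1 to end of study for all vaccine groups". Protocol 8.1.2.3 sets matching endpoint periods, to Day 181 for follow-on and Day 241 for naive subjects, and expresses the endpoints as percentages of subjects.

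The window differs in length between the two kinds of group. The Protocol Synopsis says that "The study duration is 180 days for all follow-on subjects, and 240 days for naive subjects", and its safety paragraph says that these events "will be collected for the duration of the study (180 days for follow-on subjects and 240 days for naive". The number of doses differs too. On the follow-on side Protocol 3.1 plans "for the follow on subjects one IM injection on Visit Day 1". Its plan on the other side is "for the naive subjects two IM injections on Visits Day 1 and Day 61".

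Protocol 2.2.2 has three secondary safety objectives. The first covers the MenABCWY booster "and after a first dose of MenABCWY in naive subjects". The second is its rMenB+OMV counterpart. The third covers two doses of either vaccine in naive subjects.

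Elsewhere the SAP does separate the doses. Section 13.3 gives any and related unsolicited AEs for Day 1-31 in all groups, with Day 61-91 separate for naive groups. Section 13.2 reports solicited AEs after the first vaccination apart from those after the second.

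**The concern.** For SAEs, medically attended AEs and AEs leading to withdrawal, the only naive figure listed pools events after both doses. It serves objective 3. It does not supply the first-dose figure that objectives 1 and 2 name.

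The tables will set the six groups side by side. A reader looking for a booster versus first-dose contrast would find one dose and 180 days in the follow-on columns, and two doses and 240 days in the naive columns. The direction of the distortion is predictable: with no true difference, the naive columns show more events because naive subjects are watched longer.

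**Working it through.** **Window lengths (visit schedules in the Protocol Synopsis and 3.1).**
- Follow-on: 181 − 1 = 180 days. Naive: 241 − 1 = 240 days. Both reproduce the stated durations.
- Naive, first dose only: 61 − 1 = 60 days. Naive, after dose 2: 241 − 61 = 180 days.
- Ratio of observation time: 240 / 180 = 1.33. The final calls have a ±14-day window, so the extremes are (241 − 14 − 1) / (181 + 14 − 1) = 226 / 194 = 1.16 and (241 + 14 − 1) / (181 − 14 − 1) = 254 / 166 = 1.53.

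**Size of the distortion.** The documents give no expected AE rates, so the 180-day risk p is an assumption taken over a range. The model assumes a constant hazard and no vaccine effect, and so captures observation time only. Naive risk at 240 days is 1 − (1 − p)^(240/180). Matched 60-day risk is 1 − (1 − p)^(60/180).

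| Assumed 180-day risk, follow-on | Same hazard over 240 days, naive | Difference (points) | Risk ratio | Matched 60-day risk, either group |
|---|---|---|---|---|
| 1% | 1.3% | 0.3 | 1.33 | 0.3% |
| 5% | 6.6% | 1.6 | 1.32 | 1.7% |
| 10% | 13.1% | 3.1 | 1.31 | 3.5% |
| 20% | 25.7% | 5.7 | 1.29 | 7.2% |
| 30% | 37.8% | 7.8 | 1.26 | 11.2% |

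Over a matched 60-day window the observation ratio is 60 / 60 = 1.00, and an equal hazard gives equal percentages.

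**Effect of the Day 61 visit window.** The time and events table for naive groups allows −7/+10 days, so dose 2 can fall between nominal Day 54 and Day 71. If the first-dose window ends at the earlier of the day before dose 2 and Day 60, a naive subject vaccinated on Day 54 contributes 53 days and one vaccinated on Day 61 or later contributes 60. The remaining imbalance is at most 53 / 60 = 0.88 for such a subject, and person-time makes it visible.

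**Feasibility.** SAP 13.3 assigns unsolicited AEs to intervals by day of onset. SAP 8.8 ties each AE to the most recent vaccination. Both added tables can be built from these variables.

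**The case against.** Five points can be made for the plan as it stands.

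1. A reader might infer that the first-dose part of objectives 1 and 2 goes wholly unanswered. The documents do not support that. Solicited AEs after vaccination 1 and unsolicited AEs over Day 1-31 have matched windows in all groups. SAEs and medically attended AEs with onset by Day 31 are counted within the latter, though not shown as separate categories. The gap is confined to the three long-window categories.

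2. A reader might infer a biased formal comparison. None is planned. The safety objectives ask to evaluate, whereas the immunogenicity objectives that intend a contrast say so, and Protocol 8.4.3.3.4 has no safety hypothesis. This stands: the risk lies in interpretation, and no error rate is affected.

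3. Unequal follow-up is deliberate, being six months after the last dose, and the full naive window is right for objective 3. This stands, and nothing here asks for follow-up to change.

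4. More intervals may be planned. Protocol 8.4.2.3.3 promises AE summaries by interval, and SAP 8.2.1 announces intervals for unsolicited AEs. No list follows in the text available, which may be a loss in reading the PDF, so the point does not rest on its absence. It rests on SAP 13.3, which states the window for each of these categories explicitly.

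5. It is tempting to set the 180 days after naive dose 2 against the 180 days after the booster, or to rely on an overall person-time rate. Neither answers a first-dose question. The post-dose-2 table contains only subjects who received dose 2, and Protocol 4.3 bars further vaccination after events such as a related SAE or an immediate allergic reaction, so that group is selected. An overall rate still pools both doses.

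**Conclusion.** The point holds in a limited form. For SAEs, medically attended AEs and AEs leading to withdrawal, SAP 13.3 specifies one window that covers 180 days and one dose in follow-on subjects but 240 days and two doses in naive subjects. The naive first dose is not isolated for these categories.

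The numerical effect depends on assumed risks and a constant hazard. At a 180-day risk of 1% the naive excess is 0.3 percentage points, which is negligible. At 20 to 30% it is 5.7 to 7.8 points, enough to mislead a descriptive reading. So it matters mainly if medically attended AEs prove common. Any effect of the second dose itself is outside this calculation.

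**What to change.** Keep the end-of-study tables, which suit objective 3. Add to SAP 13.3, for these three categories:

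- A matched first-dose window in all groups. For naive subjects it runs from Day 1 to the earlier of the day before dose 2 or nominal Day 60. For follow-on subjects it runs from Day 1 to Day 60. Show person-time beside the percentages.
- Naive events by most recent vaccination, with a note that the post-dose-2 table covers only subjects who received dose 2.
- A sentence that any descriptive booster versus first-dose statement rests on the matched window.

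The cost is a few extra tables, with no new data, visit or change in conduct. The drawback is fewer events in the shorter window: under the assumptions above, a 10% risk over 180 days becomes 3.5% over 60 days, so the matched figures will be less precise.
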